2.2.1 Risk Assessment

Table 2-1 Risk Assessment

Potential Risk of Clinical Significance	Summary of Data/Rationale for Risk	Mitigation Strategy
Study Intervention RESP301		
Participants need to be discontinued from supplemental oxygen for up to 4 minutes to receive nebulized study treatment	Study treatment is to be administered via a hand-held mesh nebulizer (Philips InnoSpire Go) which is designed for oral inhalation. In addition, as NO spontaneously reacts with O ₂	Participants unable to be safely discontinued from supplemental oxygen will be excluded (Exclusion criterion 2)

Potential Risk of Clinical Significance	Summary of Data/Rationale for Risk	Mitigation Strategy
	to produce NO ₂ (a bronchial irritant), it is potentially unsafe to use both treatments concomitantly	Treatment administration is to be performed as quickly as possible (Section 1.3) Oxygen saturation (SpO ₂) and heart rate will be monitored throughout the study intervention administration (Section 1.3) Stopping rules to resume supplemental O ₂ in case of decrease in SpO ₂ or clinical signs of intolerance (Section 7.1)
Risk of methemoglobinemia	Very low levels are produced but as methemoglobinemia has been reported with continuous NO gas administration, the risk cannot be firmly ruled out	Participants with a history of methemoglobinemia will be excluded (Exclusion criterion 4) and methemoglobin (mHb) is included in safety laboratory tests (Section 1.3)
Risk of clinical bronchial hyper-responsiveness related to nebulization	Excipients in the nebulized RESP301 include mannitol which is a known bronchial irritant and may potentially cause or exacerbate cough or bronchospasm	Participants with a known history of moderate or severe bronchial hyperreactivity (such as in asthma) or presence of signs of significant bronchospasm on examination will be excluded from study participation (Exclusion criterion 5)

Potential Risk of Clinical Significance	Summary of Data/Rationale for Risk	Mitigation Strategy
Study Procedures		
Nebulization	The delivered dose of RESP301, estimated to be ~40% of the masses listed in Table 6-2 , can be affected by patient technique and inspiratory capacity leading to inter- and intra-patient variation in actual doses of these ingredients, given the acute nature and high disease burden in this proposed clinical setting	Training will be provided to study staff to minimize variation in dose
Other		

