2.2.1 Risk Assessment

Table 2-1 Risk Assessment

Potential Risk of Clinical Significance	Summary of Data/Rationale for Risk	Mitigation Strategy
Study Intervention RESP301		
Participants may need to be discontinued from supplemental oxygen for	Study treatment is to be administered via a vibrating mesh nebulizer which is designed for oral inhalation.	Participants unable to be safely discontinued from supplemental oxygen will be

Potential Risk of Clinical Significance	Summary of Data/Rationale for Risk	Mitigation Strategy
several minutes to receive nebulized study treatment		
excluded (Exclusion criterion 2)
 
Treatment administration is to be performed as quickly as possible (Section 1.3)
 
Oxygen saturation (SpO₂) and heart rate will be monitored throughout the study intervention administration (Section 1.3)
 
In case of decrease in SpO₂ or clinical signs of intolerance to nebulization, RESP301 treatment may be paused temporarily and supplemental O₂ resumed or the study treatment may be discontinued permanently (see Section 7.1) per Investigator assessment.

Risk of methemoglobinemia	Very low levels are produced but as methemoglobinemia has been reported with continuous NO gas administration, the risk cannot be firmly ruled out	Participants with a history of methemoglobinemia will be excluded (Exclusion criterion 4) and methemoglobin (mHb) is included in safety laboratory tests (Section 1.3)
Risk of clinical bronchial hyper-responsiveness related to nebulization	Excipients in the nebulized RESP301 include mannitol which is a known bronchial	Participants with a known history of moderate or severe bronchial hyperreactivity

Potential Risk of Clinical Significance	Summary of Data/Rationale for Risk	Mitigation Strategy

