	
irritant at the average dose of a positive mannitol test (239.0 ± 185.0 mg, Brannan et al, 2005). While the dose used in this study (54.66 mg) is lower than the average dose for a positive mannitol test, it has not yet been tested in COVID-19 patients and may potentially cause or exacerbate cough or bronchospasm in susceptible individuals in this specific population
	
(such as in asthma) or presence of signs of significant bronchospasm on examination will be excluded from study participation (Exclusion criterion 5)
 
For the first 10 participants treated before the first IDMC safety review (Section 9.6), RESP301 will be administered by intermittent inhalation until the intended dose is delivered (Section 6.1), so that the treatment can be quickly adjusted and rescue bronchodilator initiated if needed (Section 6.5.1)
 
After reviewing safety data, the IDMC will decide whether the intermittent inhalation of RESP301 can be replaced by continuous inhalation.

Study Procedures		
Nebulization	
The delivered dose of RESP301, estimated to be ~40% of the masses listed in Table 6-2, can be affected by patient technique and inspiratory capacity leading
	
Training will be provided to study staff to minimize variation in dose

Potential Risk of Clinical Significance	Summary of Data/Rationale for Risk	Mitigation Strategy
	to inter- and intra-patient variation in actual doses of these ingredients, given the acute nature and high disease burden in this proposed clinical setting	
Other		
Risk of spreading SARS-CoV-2	SARS-CoV-2 is known to be transmissible via respiratory droplets and any interventions that may potentially increase cough or aerosolization of respiratory secretions of an infected patient may increase risk of spread of disease	Proper personal protective equipment including appropriate mask, face shield, gown and gloves should be used at all times. When possible, the site staff should not remain in the room during study intervention administration (providing that continuous O ₂ monitoring can be conducted remotely and study intervention can be administered correctly)

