5.3 Exclusion Criteria

Participants are excluded from the study if any of the following criteria apply:

Medical Conditions

1. Rapidly deteriorating or likely to require escalation to high flow oxygen, invasive or non-invasive ventilatory support within 24 hours according to Investigator's opinion.
2. Unable to safely receive a nebulized treatment for approximately 4 minutes according to Investigator's opinion.
3. Unable to receive or considered ineligible for invasive or non-invasive ventilatory support.
4. History of methemoglobinemia.
5. Uncontrolled asthma or history of severe bronchospasm.
6. Severe (requiring baseline oxygen therapy > 12 h/day prehospitalization) chronic respiratory disease (e.g., known COPD, pulmonary arterial hypertension, idiopathic pulmonary fibrosis, interstitial lung disease).
7. Suspected or confirmed untreated, active tuberculosis.
8. Severely immune-compromised participants in Investigator's opinion.
9. Recent (within 3 months) active coronary artery disease or decompensated heart failure (New York Heart Association class 3-4).
10. Presence of tracheostomy.

Prior/Concomitant Therapy

11. Chronic (≥ 4 weeks) use of corticosteroids > 10 mg/day of prednisone or equivalent within 4 weeks of randomization.

Prior/Concurrent Clinical Study Experience

12. Participation in other clinical investigations utilizing investigational treatment or within 30 days / 5 half-lives whichever is longer.

Diagnostic Assessments

13. Clinically significant abnormalities in clinical chemistry or hematology at screening, defined as:

- Platelet count <50,000 mm³
- Alanine aminotransferase or aspartate aminotransferase >5 × upper limit of normal (ULN).
- Estimated glomerular filtration rate <30 mL/min/1.73 m² (modification of diet in renal disease formula) or requiring hemofiltration or dialysis.

Other Exclusions

14. Anticipated transfer to another hospital which is not a study site during the treatment period.
15. Allergy to any of the components of the study intervention.

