** Inhaled citric acid and inhaled mannitol provoke bronchospasm in patients with bronchial hyperresponsiveness in a dose dependent pattern. Although the concentrations of mannitol and citric acid are below the provocative dose and concentration inducing bronchospasm, there is a theoretical risk that a participant may develop acute bronchospasm during the use of RESP301. Participants should therefore be monitored during RESP301 administration. In case of clinical intolerance or saturation decrease, nebulization should be immediately discontinued (see Section 7.2). Further clarification of the differences in signs and symptoms for acute bronchospasm and COVID-19 progression are provided in Table 7-1.*

Table 7-1 Differences in Signs and Symptoms for Acute Bronchospasm and COVID-19 Progression

	Acute bronchospasm related to inhaled bronchial irritant	Progression of COVID-19 lung disease to acute respiratory failure
Mechanism	Acute contraction of bronchial muscles resulting in bronchial obstruction resulting in increased ventilatory load	Cytokine storm resulting in alveolar damage resulting in gas transfer impairment
Onset	Within minutes (<15 minutes) following inhalation (no late phase since it is not an allergic IgE mediated reaction)	Within hours or days and not related to nebulization
Clinical auscultatory signs	Wheezing (almost all cases)	Bilateral rales (inconstant)
Patient history	Asthma or respiratory allergy	Age > 65 years, increased BMI, high blood pressure, cardiac diseases, etc.
Reversibility with inhaled beta mimetics	Within minutes	No

Abbreviations: BMI=body mass index; IgE=immunoglobulin E.

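### The risk table credits exclusion criterion 5 with keeping out moderate bronchial hyperreactivity and current bronchospasm, but criterion 5 covers neither (protocol versions 1.0 and 2.0)

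*Protocol*

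**What the plan says.** Section 2.2.1, Table 2-1, lists bronchial hyper-responsiveness related to nebulization as a risk of RESP301 because the product contains mannitol. The version 1.0 table gives this mitigation, citing exclusion criterion 5: "known history of moderate or severe bronchial hyperreactivity (such as in asthma) or presence of signs of significant bronchospasm on examination will be excluded". Version 2.0 keeps this sentence, beginning "Participants with a known history of moderate or severe bronchial hyperreactivity", with the same cross-reference. It adds staggered dosing and rescue bronchodilator for the first 10 participants.

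Section 5.3, criterion 5, has the same wording in both versions: "Uncontrolled asthma or history of severe bronchospasm".

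The nearest other criterion is number 2, which in version 2.0 begins "Unable to safely receive a nebulized treatment for approximately 4 minutes" and is decided by the investigator's opinion. Table 2-1 cites criterion 2 for a different risk, the interruption of supplemental oxygen.

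The footnote to Section 7.1 in version 2.0 explains why airway reactivity matters: "Inhaled citric acid and inhaled mannitol provoke bronchospasm in patients with bronchial hyperresponsiveness in a dose dependent pattern". On the chance of acute bronchospasm with RESP301 itself, the footnote is more cautious: "Although the concentrations of mannitol and citric acid are below the provocative dose and concentration inducing bronchospasm, there is a theoretical risk". Table 7-1 gives "Asthma or respiratory allergy" as the patient history that points to irritant bronchospasm.

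**The concern.** Two parts of the same protocol version describe the same exclusion and disagree on whom it covers. The risk table presents the wider exclusion as a safety measure, and the benefit-risk conclusion in Section 2.2.3 relies on the measures taken to minimise risk. Enrolment, however, is run from Section 5.3, and waivers of the entry criteria are not permitted (Sections 5 and 8). If Section 5.3 is narrower than the table, an ethics committee or investigator reading the table will believe that a protection exists which the entry criteria do not provide.

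What is at stake is the exposure of people with reactive airways to a nebulized product containing mannitol and citric acid, in what Section 2.2.3 of version 2.0 calls a first-in-man study.

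**Working it through.** No sample-size or error-rate figure is involved, so the check is a comparison of texts within each version.

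**Table 2-1 against criterion 5, versions 1.0 and 2.0**

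| Group that Table 2-1 says is excluded | Covered by criterion 5? |
|---|---|
| Known history of severe hyperreactivity | In part, through uncontrolled asthma or a history of severe bronchospasm |
| Known history of moderate hyperreactivity | No, unless it amounts to uncontrolled asthma |
| Significant bronchospasm on examination | No; criterion 5 mentions bronchospasm only as history |

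**The rest of Section 5.3**

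- Criteria in the list: 15 in version 1.0 and 15 in version 2.0.
- Criteria naming moderate bronchial hyperreactivity: 0 of 15 in each.
- Criteria naming bronchospasm on examination: 0 of 15 in each.
- Criterion 2 can reach both groups, but it is discretionary and does not mention airway reactivity.
- Criterion 6 removes only severe chronic respiratory disease needing oxygen for more than 12 hours a day before admission.

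A patient with controlled moderate asthma passes criterion 5 as written. So does a patient who is wheezing at screening but has no history of severe bronchospasm. Table 2-1 says the first is excluded, and the second too if the bronchospasm is significant.

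**How the protocol sizes the underlying risk**

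Table 2-1 of version 2.0 gives 239.0 ± 185.0 mg as the average dose of a positive mannitol test, against 54.66 mg here. It estimates that about 40% is delivered:

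- Delivered mannitol: 0.40 × 54.66 = 21.9 mg.
- If ± denotes one standard deviation (the text does not say), the nominal dose lies (239.0 − 54.66) / 185.0 = 1.0 SD below that average.
- On the same assumption, the delivered dose lies (239.0 − 21.9) / 185.0 = 1.2 SD below.

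The dose is well below the average, but the spread around that average is wide. No event rate can be derived from these figures. The documents also do not give the share of candidates in the uncovered groups.

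**Version 3.0**

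The available text of version 3.0 stops in the Schedule of Activities, before Table 2-1 and Section 5.3. For those two places the Amendment 2.0 change table lists only the methemoglobin limit, plus unspecified minor language and format edits to the whole document. The mismatch therefore probably persists, but this cannot be confirmed.

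**The case against.** The case for leaving this alone, or treating it as a minor correction, has five parts.

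- **Superseded text.** The governing version is 3.0, and its wording cannot be read here. This stands as a limit: the contradiction is established for versions 1.0 and 2.0 only.
- **Other safeguards.** Version 2.0 has staggered dosing with pauses to look for bronchospasm, a rescue bronchodilator, SpO2 and heart-rate monitoring, stopping rules and a recheck of clinical status on Day 1. The Section 7.1 footnote calls the risk theoretical. These points reduce the consequence. However, monitoring and stopping rules act only once dosing has begun, and staggering and rescue are assured only until the first IDMC review.
- **Criterion 2.** A patient in obvious bronchospasm is a natural candidate for exclusion under it. That is true, but it replaces a stated exclusion with a judgement.
- **Table 7-1.** It is a bedside aid for telling bronchospasm from COVID-19 progression and does not define who should be excluded. This is fair; the table shows only that the protocol links asthma in general with irritant bronchospasm.
- **Intent.** Chronic lung disease is a stratification factor in Section 6.3, and criterion 6 removes only oxygen-dependent disease. Both fit an intention to enrol milder or controlled lung disease, in which case Table 2-1 is the text in error. This is a real possibility and bears on which text to change. It does not remove the contradiction.

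**Conclusion.** The concern holds. In versions 1.0 and 2.0, Table 2-1 attributes to criterion 5 an exclusion wider than criterion 5 contains. The uncovered groups are moderate hyperreactivity that is controlled, and current bronchospasm without a qualifying history; severe hyperreactivity is only partly covered. None of the 15 criteria in either version names the two uncovered groups.

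The consequence is confined to participant safety, and its size cannot be quantified from the documents. The correction should be made because an eligibility rule and the safety rationale built on it disagree. Persistence in version 3.0 is an inference from its change log.

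**What to change.** First check Table 2-1 and Section 5.3 in version 3.0. If the mismatch is still there, decide which group is meant and align the two texts.

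- **If Table 2-1 is right,** amend criterion 5 to exclude: *uncontrolled asthma; a past episode of severe bronchospasm; known bronchial hyperreactivity of moderate or greater degree; or significant bronchospasm found at the screening examination or the Day 1 recheck*.
- **If criterion 5 is right,** correct Table 2-1 to match it, and state that the remaining mitigation rests on criterion 2, monitoring and the stopping rules. Whether rescue bronchodilator stays available after the first safety review remains the IDMC's decision, as the Rescue Medication section provides.

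Either way the change is one line of wording. No new procedure is needed, because the full screening examination already covers the respiratory system and clinical status is already rechecked before the first dose. Widening criterion 5 may add some screen failures, in a number the documents do not allow us to estimate. Because Section 5.5 does not allow rescreening, a patient with significant but transient bronchospasm at screening would be lost to the trial. The sponsor should weigh that when choosing between the two.

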1.3 Schedule of Activities (SoA)

Table 1-1 Schedule of Activities (SoA)

Procedure	Screening (up to 48 hours before Day 1 ¹)	Intervention Period			Early withdrawal	Efficacy follow-up (Day 14) ² (± 2 days)	EoS efficacy and safety follow-up (Day 28) ² (± 2 days)	Notes
		Day 1 ¹	Daily while hospitalized	Day 10 / hospital discharge				
Informed consent	X							Optional tokenization ICF to be provided for a subset of participants in the United States (see Section 8.4)
Confirmation of COVID-19 infection by nasopharyngeal RT-PCR ³	X							
Inclusion and exclusion criteria	X	X						Recheck clinical status before 1st dose of study intervention
Demographics	X							
Physical examination including height and weight	X			X	X		X ²	Full physical exam and height only at screening

Procedure	Screening (up to 48 hours before Day 1 ¹)	Intervention Period			Early withdrawal	Efficacy follow-up (Day 14) ² (± 2 days)	EoS efficacy and safety follow-up (Day 28) ² (± 2 days)	Notes
		Day 1 ¹	Daily while hospitalized	Day 10 / hospital discharge				
Pregnancy test (urine)	X							All women, including women of childbearing potential and pregnant women, may be enrolled in the study. Pregnancy status should be recorded (see Section 8.3.5). Note: Only females of child bearing potential and pregnant females need to undergo a screening pregnancy test.
Medical history (includes substance usage)	X							History of substance usage or abuse to be recorded but is not exclusionary
Medication history	X							In the prior 3 months
Laboratory assessments (including liver chemistries) ⁴	X	X	X ⁴	X	X		X ²	
12-lead ECG	X							After resting supine for approximately 5 minutes. QRS, QT, QTcF, PR, RR, rate
Vital signs ⁵	X	X	X ⁵	X	X		X	Within 15 minutes prior to study intervention administration
Randomization		X						

Procedure	Screening (up to 48 hours before Day 1 ¹)	Intervention Period			Early withdrawal	Efficacy follow-up (Day 14) ² (± 2 days)	EoS efficacy and safety follow-up (Day 28) ² (± 2 days)	Notes
		Day 1 ¹	Daily while hospitalized	Day 10 / hospital discharge				
Study intervention, TID ⁶		X	X	X				A staggered dosing approach will be used for the first 10 participants (up to the first IDMC safety review). Each RESP301 dose will be administered by intermittent inhalation to monitor the tolerability and response to RESP301 (see Sections 6.1 and 9.6). Where possible study intervention should be administered at approximately the same times each day At least 6 hours between 2 consecutive doses

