AE/SAE review	X	X	X	X	X	X	X	
Concomitant medication review	X	X	X	X	X	X	X	
Oxygen / respiratory assessment ⁷	X	X	X	X				
SpO ₂ on room air (after at least 1 minute) prior to study intervention administration and immediately at the end of nebulization ⁶		X	X	X				See Section 8.1.2
Modified WHO ordinal scale	X	X	X	X		X	X	See Section 8.1.1

Procedure	Screening (up to 48 hours before Day 1 ¹)	Intervention Period			Early withdrawal	Efficacy follow-up (Day 14) ² (± 2 days)	EoS efficacy and safety follow-up (Day 28) ² (± 2 days)	Notes
		Day 1 ¹	Daily while hospitalized	Day 10 / hospital discharge				
NEWS 2 assessment ⁷		X	X	X				Prior to study intervention in the morning. See Section 8.1.3

Abbreviations: AE=adverse event; aPTT= activated partial thromboplastin time; CBC=complete blood count; Chem 7=blood chemistry panel (sodium, potassium, chloride, bicarbonate/CO₂, blood urea nitrogen, creatinine, glucose); CV=cardiovascular; ECG=electrocardiogram; LFTs=liver function tests; mHb=methemoglobin; PT/INR=prothrombin time/international normalized ratio; RT-PCR=reverse transcription-polymerase chain reaction; SAE=serious adverse event; TID=three times daily.

1. Screening and randomization may be on the same day, providing all eligibility criteria are met.
2. For participants who are already discharged at either the Day 14 or Day 28 (EoS) follow-up, there will be a phone call to check AEs/SAEs, concomitant medications, and modified WHO ordinal scale. At EoS, safety laboratory tests (nitrite and mHb only) and weight will be collected for participants in hospital only.
3. COVID-19 infection must be confirmed and documented in chart with a positive result on a validated test.
4. At Screening: CBC, chem 7, mHb, LFTs, coagulation (PT/INR, aPTT).
On Day 1, Day 3, Day 7 and Day 10, or early withdrawal: CBC and chem 7 (per SOC).
On Day 28: nitrite and mHb (participants in hospital at EoS only).
5. Vital signs: temperature, heart rate, blood pressure, respiratory rate. Vital signs to be repeated as per SOC during treatment period.
6. Study intervention comprises the following procedures which are to be done in order and as quickly as possible:
 - a. Recording of oxygen flow level including mode (nasal cannula, mask)
 - b. Recording of SpO₂ and heart rate
 - c. Discontinuation of supplemental oxygen administration *
 - d. Close participant oversight by trained health care professional until SpO₂ is stable on ambient air after one minute at least *

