10.3 Appendix 3: Clinical Laboratory Tests

The tests detailed in Table 1-1 will be performed by the local laboratory.

Protocol-specific requirements for inclusion or exclusion of participants are detailed in Section 5 of the protocol. Additional tests may be performed at any time during the study as determined necessary by the Investigator or required by local regulations.

Table 10-1 **Protocol-Required Laboratory Assessments**

Laboratory Assessments	Parameters			
Hematology	
CBC without differential:
 
White blood cell (WBC) count, red blood cell (RBC) count, hemoglobin, hematocrit, mean corpuscular volume, mean corpuscular hemoglobin, mean corpuscular hemoglobin concentration, red cell distribution width, platelet, mean platelet volume
 
Methemoglobin, nitrite
			
Clinical Chemistry ¹	Blood urea nitrogen Creatinine Glucose non-fasting	Potassium Sodium Chloride Bicarbonate/CO ₂	Aspartate Aminotransferase / Serum Glutamic-Oxaloacetic Transaminase Alanine Aminotransferase/ Serum Glutamic-Pyruvic Transaminase Alkaline phosphatase / Lactate dehydrogenase	Total and direct bilirubin Coagulation (PT/INR, aPTT)
Other Screening Tests	Highly sensitive urine human chorionic gonadotropin pregnancy test (for women of childbearing potential and pregnant women) ²			

Laboratory Assessments	Parameters
	The results of each test must be entered into the eCRF.

NOTES:

1 Details of liver chemistry stopping criteria and required actions and follow-up assessments after liver stopping or monitoring event are given in Section 7.1. All events of ALT $\geq 3 \times$ ULN and bilirubin $\geq 2 \times$ ULN ($>35\%$ direct bilirubin) or ALT $\geq 3 \times$ ULN and international normalized ratio (INR) >1.5 , if INR measured which may indicate severe liver injury (possible Hy's Law), must be reported as an SAE (excluding studies of hepatic impairment or cirrhosis).

2 Local urine testing will be standard for the protocol unless serum testing is required by local regulation or IRB/IEC.

Investigators must document their review of each laboratory safety report.

10.4 Appendix 4: Adverse Events: Definitions and Procedures for Recording, Evaluating, Follow-up, and Reporting

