Section 4.1 Overall Design Section 6.1 Study Intervention Administered Section 9.6 Data Monitoring Committee (DMC)	
Due to the urgency of the pandemic, if participants become eligible for the study during the IDMC review of the first 10 participants then they may be recruited. However, their administration of RESP301 will be staggered in the same way as for the first 10 participants.
 
Once the IDMC review has been completed, and provided there are no safety concerns, further recruitment will continue as per protocol. The Sponsor and contract research organization (CRO) confirm that the report from the IDMC will be sent in a timely manner to all participating sites and investigators.
	The staggered dosing approach will be used for all participants enrolled up to completion of the first IDMC safety review, to ensure appropriate safety procedures are in place for the first participants recruited into the study.
Section 6.5.1 Potential Drug Interactions	A new section was added to describe NO donor agents that may increase the risk of developing methemoglobinemia.	To ensure that investigators are aware of the potential risk of interaction between NO and other NO donor agents.
Section 7.1 Permanent Discontinuation of Study Intervention	Addition of Hy's law discontinuation criteria to the first bullet.	To ensure consistency with Appendix 10.3.
Whole document	Minor language and format changes.	For improved clarity and readability.

Table of Contents

Protocol Amendment Summary of Changes Table	3
Table of Contents	5
1 Protocol Summary	9
1.1 Synopsis.....	9
1.2 Schema	12
1.3 Schedule of Activities (SoA).....	13
2 Introduction.....	18
2.1 Background.....	18
2.2 Benefit/Risk Assessment	21
2.2.1 Risk Assessment	21
2.2.2 Benefit Assessment.....	24
2.2.3 Overall Benefit: Risk Conclusion.....	26
3 Objectives and Endpoints	26
4 Study Design.....	27
4.1 Overall Design.....	27
4.2 Scientific Rationale for Study Design	29
4.3 Justification for Dose.....	30
4.4 End of Study Definition.....	30
5 Study Population.....	30
5.1 Study Rationale	30
5.2 Inclusion Criteria	31
5.3 Exclusion Criteria.....	32
5.4 Lifestyle Considerations	33
5.5 Screen Failures	33
5.5.1 Screening and Enrollment Log and Participant Identification Numbers.....	33
6 Study Intervention	34
6.1 Study Intervention Administered.....	34
6.1.1 Medical Devices	35
6.1.2 Device Training	36

6.2	Preparation, Handling, Storage, and Accountability	36
6.2.1	Preparation of Study Intervention Product	36

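### The schedule's laboratory row names liver tests during treatment but its footnote lists them at screening only, and the protocol does not settle what happens when an eligible patient already meets the liver SAE combination at entry

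*Protocol*

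**What the plan says.** Section numbers refer to the Amendment 1 text (Version 2.0) unless stated otherwise. Version 3.0 is known here mainly through its summary of changes.

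- **Schedule, Section 1.3, Table 1-1.** The row "Laboratory assessments (including liver chemistries" is marked at screening, Day 1, daily while in hospital, Day 10 or discharge, early withdrawal and Day 28.
- **Schedule, footnote 4.** Screening includes liver function tests and PT/INR. For treatment it reads "On Day 1, Day 3, Day 7 and Day 10, or early withdrawal: CBC and chem 7 (per SOC". Day 28 is nitrite and methemoglobin (mHb), for participants still in hospital. The abbreviation list defines chem 7 as electrolytes, bicarbonate, urea nitrogen, creatinine and glucose.
- **Entry, Section 5.3.** Exclusion 13 opens with "Clinically significant abnormalities in clinical chemistry or hematology at screening, defined as" and then lists platelets, "Alanine aminotransferase or aspartate aminotransferase >5 × upper limit of normal (ULN" and kidney function. No exclusion names bilirubin, INR or liver disease.
- **Reporting, Appendix 3, note 1.** ALT ≥3×ULN with bilirubin ≥2×ULN (more than 35% direct), or ALT ≥3×ULN with INR >1.5, "if INR measured which may indicate severe liver injury (possible Hy's Law), must be reported as an SAE". The limits are absolute. The note sends the reader to Section 7.1 for liver stopping criteria.
- **Stopping, Section 7.1.** Stopping for abnormal liver tests is left to the Investigator's judgement. The Amendment 2.0 summary of changes records "Addition of Hy's law discontinuation criteria to the first bullet" for this section.

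**The concern.** Two things do not fit together. First, the protocol has a liver reporting rule, a liver stopping provision and planned laboratory change-from-baseline summaries (Section 9.4.5.2), all of which need liver values after baseline. Footnote 4 schedules none. If sites follow the footnote, on-treatment liver data come only from tests done for clinical reasons. In an open-label trial such testing need not be the same in both arms, so the liver comparison would rest on an unplanned and possibly uneven sample of patients.

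Second, the entry limit is wider than the ALT part of the reporting combination, and entry carries no bilirubin or INR condition. A patient can be properly enrolled while already meeting the combination, and sites could classify the same screening result differently depending on which section they read.

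**Working it through.** The protocol gives no figure to reproduce. The check compares thresholds, then compares the tests the rule needs with the tests scheduled.

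**Step 1: entry limit against reporting combination.**

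- Eligible: ALT ≤5×ULN and AST ≤5×ULN.
- Combination: ALT ≥3×ULN and (bilirubin ≥2×ULN with direct fraction >35%, or INR >1.5).
- Intersection: 3×ULN ≤ ALT ≤ 5×ULN, with either partner abnormality.

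Trial values, taking AST as 1×ULN and the direct fraction as 40% in the raised-bilirubin cases:

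| ALT (×ULN) | Eligible? | Met with bilirubin 2 or 10×ULN? | Met with INR 1.6 or 3.0? |
|---|---|---|---|
| 2.9 | yes | no | no |
| 3, 4, 5 | yes | yes | yes |
| 5.1 | no | yes | yes |

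With bilirubin at 1×ULN and INR at 1.0 the combination is not met at any of these ALT values. The whole band from 3 to 5×ULN is therefore admissible together with a qualifying bilirubin or INR.

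**Step 2: tests needed against tests scheduled.** The rule needs three tests: ALT, bilirubin and INR.

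| Visit | Row marked? | Footnote 4 panel | Needed tests in panel |
|---|---|---|---|
| Screening | yes | CBC, chem 7, mHb, LFTs, coagulation | 3 of 3 |
| Day 1 | yes | CBC, chem 7 | 0 of 3 |
| Days 3 and 7 | yes (daily column) | CBC, chem 7 | 0 of 3 |
| Day 10 | yes | CBC, chem 7 | 0 of 3 |
| Early withdrawal | yes | CBC, chem 7 | 0 of 3 |
| Day 28 | yes | nitrite, mHb | 0 of 3 |

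The Amendment 2.0 summary adds only mHb to footnote 4 and only mHb >1% to exclusion 13, so on what it lists the liver counts do not change. Its stated reason for the added mHb draws is assessment against the discontinuation criteria. It lists no corresponding change for liver tests, although the same amendment adds liver discontinuation criteria to Section 7.1.

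**Step 3: status of a qualifying screening value.** Note 1 applies to all events and is mandatory, and Section 8.3.1 collects SAEs from consent. Against that, Section 10.4.1 ties an AE to use of the study intervention. It also leaves out laboratory findings associated with the underlying disease unless more severe than expected, and fluctuations of pre-existing conditions that do not worsen. Section 10.4.2 says that what is not an AE cannot be an SAE. Both routes are open on the text.

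**The case against.** The strongest reply has four parts.

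1. *The AE definitions already deal with screening values.* A stable abnormality in an untreated patient most naturally falls outside Section 10.4.1 and so cannot be an SAE. Section 8 also allows routine tests taken before consent to serve as screening values, and these would precede SAE collection. This stands far enough to defeat a reading that a reader might infer, namely that baseline liver disease is counted as an SAE. The documents support only that it may be, because note 1 is worded without exception.

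2. *The stopping rule cannot be seen.* A reader might also infer that a just-enrolled RESP301 patient must be taken off treatment. The amended Section 7.1 wording is not shown. The change is one line in the summary, and the item in the last full text is discretionary. Nothing visible shows that the criteria are automatic or apply to an unchanged baseline value.

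3. *The row does schedule liver tests.* Appendix 3, Table 10-1, also lists ALT, bilirubin and coagulation as required, and Section 8.2.4 has clinically abnormal values repeated. So a flat statement that on-treatment liver injury has no scheduled test goes too far; it holds only under footnote 4. However, Section 8.2.4 refers to the schedule for timing, and the row label carries footnote 4. If the footnote is taken to govern its own row, the conflict fades but the data gap becomes definite. Repeats start from a value already found abnormal, so they do not replace a schedule.

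4. *Entry values are balanced by randomization in expectation.* This is right. They add noise rather than a directional bias, and laboratory data are analysed as change from baseline. That analysis, however, needs post-baseline values.

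An entry limit wider than a reporting threshold is not in itself an error. The fault is that the consequence is left open.

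**Conclusion.** The point holds in two parts.

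The firmer part is the schedule. Row and footnote do not agree, and under the footnote 0 of the 3 tests needed are scheduled after screening. The liver SAE rule, the Section 7.1 provision and the planned liver summaries would then rely on unscheduled tests or repeats of abnormal values. This depends on the footnote being the text that sites follow, and on Version 3.0 making no liver change beyond those its summary lists.

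The second part is an ambiguity, not a proven miscount. Patients with ALT of 3 to 5×ULN and a qualifying bilirubin or INR are eligible and meet the combination at entry; whether that is reported as an SAE depends on which section is applied. How many such patients there would be cannot be said. An assumed rate of 1% to 3% would give 0.01 × 300 = 3 to 0.03 × 300 = 9, but nothing in the documents supports any rate, and the conclusion does not rest on one.

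**What to change.** Two reconciliations, with the clinical limits and the choice of rule left to the sponsor:

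1. **Table 1-1 row and footnote 4.** Make them state the same liver tests at the same visits, so that the liver SAE rule, Section 7.1 and the Section 9.4.5.2 summaries rest on data the schedule provides. Check the resulting draws against the 20 mL total blood limit in Section 8.
2. **Exclusion 13, Appendix 3 note 1, Sections 10.4.1 and 10.4.2, and Section 7.1.** Reconcile these so that it is clear whether a patient who meets the combination at screening is eligible, whether the value is reported as an SAE, and how it bears on the discontinuation provision.

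The cost is mainly amendment wording. ALT, bilirubin and INR are already obtained at screening, so the entry question needs no new test. Any analytes added later would go on draws already listed, subject to the blood limit. Depending on the sponsor's choice, some borderline patients might become ineligible.
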